5.2.1. Analyses for Binary Endpoints

Descriptive statistics for the binary variables (eg, proportions) are the percentage (%), the numerator (n) and the denominator (N) used in the percentage calculation, and the 95% CIs where applicable.

The exact 95% CI for the binary endpoints of each group will be computed using the F distribution (Clopper and Pearson method).³ The 95% CI for the between-group difference for binary endpoints will be calculated using the Miettinen and Nurminen method.⁴

5.2.1.1. Safety Data

All safety analyses will be performed on the safety populations.

For safety data, as defined in Section 3.1.1, the exact 2-sided 95% CIs using the Clopper and Pearson method will be provided by vaccine group for all primary safety endpoints and for proportions of participants reporting local reactions, systemic events, AEs (including immediate AEs), SAEs, abnormal troponin I values, and new ECG abnormalities. The 95% CI for the between-group difference for binary endpoints will be calculated using the Miettinen and Nurminen method.

5.2.1.2. Immunogenicity Data

The proportion of participants achieving HAI seroconversion at each time point after each vaccination, and the proportion of participants with HAI titers ≥1:40 before each vaccination and at each time point after each vaccination, and associated 2-sided Clopper-Pearson 95% CIs will be provided by vaccine group for each strain, all strains, and each heterologous strain.

5.2.2. Analyses for Continuous Endpoints

Unless otherwise stated, descriptive statistics for the continuous variables are n, mean, median, standard deviation, minimum, and maximum.

5.2.2.1. Geometric Means

The geometric mean will be calculated as the mean of the assay results after making the logarithm transformation and then exponentiating the mean to express results on the original scale. Two-sided 95% CIs will be obtained by taking log transforms of assay results, calculating the 95% CI with reference to Student's t distribution, and then exponentiating the confidence limits. When multiple records are available, the average of the records will be calculated as the value to be analyzed. The records from the same run will be paired and analyzed. For example, the same-run baseline record will be paired with postvaccination records to calculate the seroconversions.

5.2.2.2. Geometric Mean Fold Rises

GMFRs are defined as ratios of the results after vaccination to the results before vaccination. GMFRs are limited to participants with nonmissing values at both time points. When prevaccination assay results are lower than the LLOQ and the postvaccination results are greater than or equal to the LLOQ, the prevaccination assay results will be set to LLOQ for the GMFR calculation.

GMFRs will be calculated as the mean of the difference of logarithmically transformed assay results (later time point minus earlier time point) and exponentiating the mean. The associated 2-sided 95% CIs will be obtained by constructing CIs using Student's t distribution for the mean difference on the logarithm scale and exponentiating the confidence limits.

For example, HAI GMFRs will be calculated as the mean difference of logarithmically transformed assay results from before vaccination to each time point after vaccination, and associated 2-sided 95% CIs, will be provided by vaccine group.

5.2.2.3. Geometric Mean Ratios

The GMR will be calculated as the mean of the difference of logarithmically transformed assay results and exponentiating the mean. Two-sided CIs will be obtained by calculating CIs using Student's t distribution for the mean difference of the logarithmically transformed assay results and exponentiating the confidence limits.

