9.3.1. General Considerations

CIs for all endpoints in the statistical analysis will be presented as 2-sided at the 95% level unless specified otherwise.

The safety analyses are based on the safety population. Participants will be summarized by vaccine group according to the study interventions they actually received. Completely missing reactogenicity e-diary data will not be imputed; missing AE dates will be handled according to the Pfizer safety rules.

For all the immunogenicity endpoints, the analysis will be based on the evaluable immunogenicity population. Antibody titers below the LLOQ or denoted as BLQ will be set to $0.5 \times \text{LLOQ}$ for GMT analysis. No other missing assay data will be imputed in the analyses. All immunogenicity analyses will be performed after the imputation of the antibody concentrations or antibody titers that are below the LLOQ.

An additional analysis may be performed based on the mITT populations if there is a large enough difference in sample size between the mITT population and the evaluable immunogenicity population. Participants will be summarized according to the vaccine group to which they were randomized. Missing serology data will not be imputed.

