9.3.1.2.2. Geometric Mean Fold Rises

GMFRs are defined as ratios of the results after vaccination to the results before vaccination. GMFRs are limited to participants with nonmissing values at both time points.

GMFRs will be calculated as the mean of the difference of logarithmically transformed assay results (later time point minus earlier time point) and exponentiating the mean. The associated 2-sided 95% CIs will be obtained by constructing CIs using Student's t-distribution for the mean difference on the logarithm scale and exponentiating the confidence limits.

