9.3.1.2.3. Geometric Mean Ratios

The GMR will be calculated as the mean of the difference of logarithmically transformed assay results and exponentiating the mean. Two-sided CIs will be obtained by calculating CIs using Student's t-distribution for the mean difference of the logarithmically transformed assay results and exponentiating the confidence limits.

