2.1. Modifications to the Analysis Plan Described in the Protocol

The following modifications were made: added 240 participants from 18 through 64 years of age, who will receive either 1 dose of CCI qIRV or 1 dose of CCI qIRV; added the primary safety, secondary, and tertiary objectives of immune responses elicited by qIRV in adults from 18 through 64 years of age and their corresponding estimands and endpoints; and removed the tertiary estimands and endpoints for all the heterologous strains.

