5.3.2. Immunogenicity Data

Any assay results above the LLOQ are considered accurate, and their quantitated values will be reported. Antibody titers below the LLOQ, denoted as BLQ, or below the LOD will be set to $0.5 \times \text{LLOQ}$ for GMT analysis. No other missing assay data will be imputed in the analyses, with the exception of that mentioned for GMFR in Section 5.2.2.2. All immunogenicity analyses will be performed after the imputation of the antibody concentrations or antibody titers that are below the LLOQ.

Values that are designated as serum QNS, IND, or "not done" will be set to missing. No imputation will be done for these missing values.

LLOQ results for each assay used in this study will be included in the analysis specification once they are available.

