- Intercurrent events and missing data: Missing immunogenicity results will not be imputed, as MCAR is assumed. For participants who discontinue or have major protocol violations, all postdiscontinuation or postviolation observations will be censored.
- Reporting results: HAI GMFRs (Section 5.2.2.2) from before Vaccination 1 to prior to Vaccination 2 (Day 21, if applicable) and to 1, 4, and 8 weeks after receipt of the last vaccination, and associated 2-sided 95% CIs, will be provided by vaccine group and strain(s).

6.2.1.1.3. The Proportion of Participants Achieving HAI Seroconversion for Each Strain at Each Time Point After Receipt of Vaccination 1

6.2.1.1.3.1. Main Analysis

- Estimand: The proportion of participants achieving HAI seroconversion for each strain prior to Vaccination 2 (Day 21, if applicable) and at 1, 4, and 8 weeks after receipt of the last vaccination.
- Estimand strategy: Hypothetical strategies (Section 2.2.2).
- Analysis set: Evaluable immunogenicity population (Section 4).
- Analysis time points: Prior to Vaccination 2 (Day 21, if applicable) and at 1, 4, and 8 weeks after receipt of the last vaccination.
- Analysis methodology: Descriptive summary statistics.

- Intercurrent events and missing data: Missing immunogenicity results will not be imputed, as MCAR is assumed. For participants who discontinue or have major protocol violations, all postdiscontinuation or postviolation observations will be censored.
- Reporting results: The proportion of participants achieving HAI seroconversion for each strain and associated 2-sided Clopper-Pearson 95% CIs will be provided by vaccine group prior to Vaccination 2 (Day 21, if applicable) and at 1, 4, and 8 weeks after receipt of the last vaccination.

Figures:

Bar charts with the numbers, proportions, and associated 95% CIs of participants achieving HAI seroconversion for each strain prior to Vaccination 2 (Day 21, if applicable) and at 1, 4, and 8 weeks after receipt of the last vaccination, and associated 2-sided Clopper-Pearson 95% CIs, will be plotted by vaccine group.

6.2.1.1.4. The Proportion of Participants With HAI Titers ≥1:40 for Each Strain Before Vaccination 1 and at Each Time Point After Vaccination 1

6.2.1.1.4.1. Main Analysis

- Estimand: The proportion of participants with HAI titers ≥1:40 for each strain before Vaccination 1, before Vaccination 2 (Day 21, if applicable), and at 1, 4, and 8 weeks after receipt of the last vaccination.

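### The readable GMR method leaves out the Day 1 HAI titer, and the GMFR rule gives a below-LLOQ baseline a value that depends on the post-vaccination result

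*SAP*

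**What the plan says.** **GMR.** SAP 5.2.2.3 says: "The GMR will be calculated as the mean of the difference of logarithmically transformed assay results and exponentiating the mean". Protocol 9.3.1.2.3 gives the same method, with the interval from Student's "t-distribution for the mean difference of the logarithmically transformed assay results and exponentiating the confidence limits". Neither text names a covariate or a model. A pre-vaccination immunogenicity sample is scheduled for everyone (Protocol 10.9.1, Visit 1; 10.10.1 and 10.10.8.8.2, Visit 201). A GMR of qIRV against QIV at 4 weeks is a secondary analysis in Substudy A (Protocol 10.9.9.3.3). The synopsis, under Statistical Methods, also announces a GMR for selected groups across both substudies. No readable Substudy B estimand is a GMR, and the exploratory sections are blacked out.

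**GMFR.** This is a readable secondary estimand in Substudy B (Protocol 10.10.3; SAP 2.2 and 6.2.1.1.2). When the baseline is below LLOQ and the later result is at or above it, SAP 5.2.2.2 says "the prevaccination assay results will be set to LLOQ for the GMFR calculation". SAP 5.3.2 gives 0.5 x LLOQ for GMT analysis and marks the GMFR rule as an exception: "No other missing assay data will be imputed in the analyses, with the exception of that mentioned for GMFR in Section 5.2.2.2". The protocol has no such exception. Its 9.3.1 says "All immunogenicity analyses will be performed after the imputation of the antibody concentrations or antibody titers that are below the LLOQ", and its 9.3.1.2.2 adds only that "GMFRs are limited to participants with nonmissing values at both time points". SAP 2.1 begins "The following modifications were made: added 240 participants from 18 through 64 years of age" and does not mention the rule.

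**The concern.** Pre-vaccination HAI titer usually predicts post-vaccination titer. A between-group ratio that ignores it gives wider intervals than the collected data require, and this matters most in groups of 15. SAP 5.2 analyses initial and expanded enrollment separately, so 15 per group is a real analysis size.

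For the GMFR, the value given to an unquantifiable baseline is decided by the outcome. One participant can have a baseline of LLOQ at one visit and 0.5 x LLOQ at another. Upward and downward crossings of the LLOQ are not treated alike. The GMT and GMFR tables for the same participants will then disagree without explanation. The sponsor reviews unblinded data for dose selection (Protocol 10.10.9.4), and its internal committee reviews immunogenicity before a group is expanded (10.10.4.1). Descriptive estimates can therefore carry weight, although no text names the GMFR or GMR as a criterion.

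**Working it through.** **Inputs.** The documents state no numerical figure for the GMR or GMFR. The group sizes, 15 and 120, reproduce the Substudy B maximum in Protocol 9.5: 11 x 15 + 13 x 120 = 165 + 1560 = 1725. The documents give no SD, correlation, LLOQ or below-LLOQ share, so those below are assumptions.

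**GMR.** In large samples, adjusted over unadjusted interval width on the log scale is sqrt(1 - rho^2), which is 0.954/0.866/0.714 for rho 0.3/0.5/0.7. Simulated two-group trials (equal groups, bivariate normal log titers), which also charge for the extra parameter, give these ratios of mean 95% CI width:

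| rho | n = 15 per group | n = 120 per group |
|---|---|---|
| 0.1 | 1.015 | 0.997 |
| 0.2 | 1.00 | 0.98 |
| 0.3 | 0.97 | 0.96 |
| 0.5 | 0.88 | 0.87 |
| 0.7 | 0.73 | 0.72 |

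With two-fold titers and half the baselines below LLOQ, the gain shrinks: for rho 0.3/0.5/0.7 the ratios are 0.98/0.92/0.80 at n = 15 and 0.97/0.90/0.79 at n = 120.

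If groups enrolled at different times were compared and their baseline GMTs differed by a factor r, the unadjusted GMR would be off by r^b, where b is the slope of log post titer on log baseline. For b from 0.3 to 0.7 this is 1.07 to 1.17 at r = 1.25 and 1.13 to 1.33 at r = 1.5.

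**GMFR, single participants** (LLOQ 1:10 assumed; 0.5 x LLOQ read as applying wherever the exception does not):

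| Baseline to post | SAP rule | 0.5 x LLOQ at both |
|---|---|---|
| <10 to <10 | 1 | 1 |
| <10 to 10 | 1 | 2 |
| <10 to 20 | 2 | 4 |
| <10 to 40 | 4 | 8 |
| 10 to <10 | 0.5 | 0.5 |

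**GMFR, group level.** Each upward crossing lowers that participant's log2 fold rise by exactly 1. In the same participants and records, GMFR = (post GMT / pre GMT) x 2^-p, where p is the share crossing upward. This identity does not depend on the LLOQ value.

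For size, assume SD 0.5 log10, correlation 0.6 and LLOQ 10:

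| Baselines below LLOQ | 8% | 20% | 34% | 50% |
|---|---|---|---|---|
| No true change, SAP rule | 0.97 | 0.93 | 0.91 | 0.90 |
| No true change, 0.5 x LLOQ at both | 1.00 | 1.00 | 1.00 | 1.00 |
| True 4-fold, SAP rule | 3.84 | 3.53 | 3.14 | 2.67 |
| True 4-fold, 0.5 x LLOQ at both | 4.05 | 4.01 | 3.86 | 3.52 |
| Multiplier on ratio of GMFRs, 4-fold v 3-fold | 0.998 | 0.993 | 0.984 | 0.970 |
| Same, 4-fold v 1.5-fold | 0.99 | 0.965 | 0.93 | 0.89 |

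The last two rows assume equal below-LLOQ shares at baseline in both groups.

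**The case against.** **On the GMR.** This SAP governs Substudy B only (SAP 2), where no readable estimand is a GMR. The readable one belongs to Substudy A, whose qIRV group has 15 participants. Blacked-out sections may already contain an adjusted model. The unadjusted ratio is valid under concurrent randomization, and at 15 per group adjustment gains nothing when the correlation is about 0.2 or lower. All of this stands, and it limits the point to an inexpensive improvement wherever a GMR is reported. A reader might infer that the planned GMR is biased, because Protocol 10.10.4.1 and SAP 2.3.1 allow groups to be randomized at different times. No text says that a GMR against a non-concurrent comparator is planned, so bias remains conditional.

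**On the GMFR.** The rule is prespecified, marked as an exception and conservative for rises. It also has a rationale: with LLOQ 1:10, counting from LLOQ matches the seroconversion definition, which takes <1:10 to 1:40 as the threshold. Under 0.5 x LLOQ, <1:10 to 1:20 would count as a 4-fold rise that is not seroconversion. This stands and argues against replacing the rule.

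A reader might infer an unreported breach of the protocol. That is too strong. Both documents state 0.5 x LLOQ for GMT analysis, and extending it to the GMFR rests on the general sentence about imputation. Protocol Section 9 lets the SAP modify such detail, and the items in SAP 2.1 all mirror Amendment 5. Finally, SAP 5.2.2.1 pairs records from the same assay run, so with multiple records the GMFR and the tabulated GMT ratio could differ anyway. The 2^-p factor is a further, systematic difference.

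**Conclusion.** Both parts hold in limited form.

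The readable GMR method leaves a collected covariate unused. Under concurrent randomization that costs precision only: up to about 28% of interval width at a correlation of 0.7, about 12% to 13% at 0.5, 3% to 4% at 0.3, and nothing at about 0.2 with 15 per group. Confidence is limited by the redactions and the assumed correlations.

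The GMFR rule makes the baseline depend on the outcome and multiplies the GMFR by 2^-p relative to the GMT ratio. That factor is exact, given the stated reading of SAP 5.3.2. The sizes (0.97 to 0.90 under no change, and 5% to 24% lower under a true 4-fold rise) rest on the assumed SD, correlation and below-LLOQ shares. Between groups with similar responses the effect is small, at most 3% for 4-fold against 3-fold. It can reach about 10% when responses differ widely.

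Neither part affects a decision rule, because the study is descriptive with no hypotheses (Protocol 10.10.9.1; SAP 5.1). Seroconversion and titers of at least 1:40 do not use the GMFR rule. The documents do not support calling the rule an error or changing the main GMFR.

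**What to change.** **GMR.** Wherever a GMR is reported (the Substudy A secondary analysis, and any Substudy B GMR under the synopsis), and unless a redacted section already does so, fit a linear model of log post-vaccination titer on vaccine group and log Day 1 titer for that strain, with below-LLOQ values at 0.5 x LLOQ. Back-transform the group contrast and report the unadjusted GMR as supportive. Participants without a baseline titer drop out of the adjusted estimate. Sponsor staff are unblinded in both substudies (Protocol 10.9.6.2.3 and 10.10.6.2.3), so date the change and show both results.

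**GMFR.** Keep the rule in SAP 5.2.2.2 as the main analysis. Add a sensitivity GMFR with 0.5 x LLOQ at both time points, and footnote the tables to say that the GMFR need not equal the ratio of GMTs. State explicitly which value applies when both results are below LLOQ.

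**Cost.** One model statement, one extra GMFR table and a footnote, with no new data. Neither quantity is a primary endpoint, so Protocol Section 9 and SAP Section 2 do not require a protocol amendment.

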5.2.2.4. Reverse Cumulative Distribution Curves

Empirical RCDCs will plot proportions of participants with values equal to or exceeding a specified assay value versus the indicated assay value, for all observed assay values. Data points will be joined by a step function with the line first going down and then to the right to the next assay value.

5.3. Methods to Manage Missing Data

5.3.1. Safety Data

Completely missing reactogenicity e-diary data will not be imputed; missing AE dates, missing laboratory test values, and missing ECG values will be handled according to the Pfizer safety rules.

5.3.1.1. Reactogenicity Data

For derived variables based on reactogenicity data, if any day of the 7-day e-diary is available, the "any day (Day 1-7)" data will be considered nonmissing.

The reactogenicity data are collected through the e-diary, which does not allow participants to skip the question. Therefore, for a specific day, as long as the e-diary data are transferred for that day, all of the reactogenicity data for the participant on that day are nonmissing. No missing reactogenicity data will be imputed other than what is described in Section 3.1.1.1 and Section 3.1.1.2.

5.3.2. Immunogenicity Data

Any assay results above the LLOQ are considered accurate, and their quantitated values will be reported. Antibody titers below the LLOQ, denoted as BLQ, or below the LOD will be set to $0.5 \times \text{LLOQ}$ for GMT analysis. No other missing assay data will be imputed in the analyses, with the exception of that mentioned for GMFR in Section 5.2.2.2. All immunogenicity analyses will be performed after the imputation of the antibody concentrations or antibody titers that are below the LLOQ.

Values that are designated as serum QNS, IND, or "not done" will be set to missing. No imputation will be done for these missing values.

LLOQ results for each assay used in this study will be included in the analysis specification once they are available.

6. ANALYSES AND SUMMARIES

- 6.1. Primary Endpoints
- 6.1.1. Primary Safety Endpoints
- 6.1.1.1. Local Reactions

6.1.1.1.1. Main Analysis

- Estimand: The percentage of participants reporting local reactions (redness, swelling, and pain at the injection site) for up to 7 days following each vaccination (Section 3.1.1.1).
- Estimand strategy: Treatment policy (Section 2.2.1).
- Analysis set: Safety population for 1-visit schedules and Vaccination 1 safety population or Vaccination 2 safety population for 2-visit schedules (Section 4).
- Analysis time point: Day 1 through Day 7 after each vaccination. Refer to Section 3.1.1.1 for maximum severity.
- Analysis methodology: Descriptive summary statistics.
- Intercurrent events and missing data: The participants without any e-diary data throughout the 7 days after each vaccination will be excluded from the analysis at that particular vaccination. For participants who discontinue, all collected data will be included; intermediate missing values will not be imputed.
- Reporting results: The proportion, the numerator (n) and denominator (N) used for the calculation of the proportion, and associated 2-sided Clopper-Pearson 95% CI will be presented, by vaccine group, for the following variables:
 - o Presence or absence of each local reaction on each day (Day 1-7) after vaccination.
 - o Presence or absence of each local reaction on "any day (Day 1-7)" after vaccination.
 - o Presence or absence of any local reaction on "any day (Day 1-7)" after vaccination.
 - o Maximum severity of each local reaction on "any day (Day 1-7)" after vaccination.
- The n, mean, standard deviation, median, minimum, and maximum will be presented by vaccine group, for the following variables:
 - O Duration of each local reaction after vaccination.

- Onset day of each local reaction after vaccination.
- Onset day of any local reaction after vaccination.

Figures:

Bar charts with the proportions of participants for each local reaction throughout 7 days will be plotted by vaccine group. The bars will be divided into severity categories to highlight the proportions of participants by maximum severity.

6.1.1.2. Systemic Events

6.1.1.2.1. Main Analysis

- Estimand: The percentage of participants reporting systemic events (fever, fatigue, headache, chills, vomiting, diarrhea, new or worsened muscle pain, and new or worsened joint pain) for up to 7 days following each vaccination (Section 3.1.1.2).
- Estimand strategy: Treatment policy (Section 2.2.1).
- Analysis set: Safety population for 1-visit schedules and Vaccination 1 safety population or Vaccination 2 safety population for 2-visit schedules (Section 4).
- Analysis time point: Day 1 through Day 7 after each vaccination. Refer to Section 3.1.1.1 for maximum severity.
- Analysis methodology: Descriptive summary statistics.
- Intercurrent events and missing data: The participants without any e-diary data throughout the 7 days after vaccination will be excluded from the analysis at that particular vaccination. For participants who discontinue, all collected data will be included; intermediate missing values will not be imputed.
- Reporting results: Descriptive statistics for each systemic event after each dose will be presented by maximum severity and cumulatively across severity levels by vaccine group. Descriptive summary statistics will include counts and percentages of participants with the indicated endpoint and the associated 2-sided Clopper-Pearson 95% CIs.

The endpoints for assessment of systemic events will be summarized similarly to the assessment of local reactions.

The use of antipyretic medication (see Section 3.1.1.4) will be summarized similarly to systemic events, except that there is no severity level associated with the use of antipyretic medication.

Figures:

Bar charts with the proportions of participants reporting each systemic event throughout 7 days after each vaccination will be plotted by vaccine group. The bars will be divided into severity categories to highlight the proportions of participants by severity.

